- The rate of decline in FVC will be analyzed using a random coefficient regression model (linear slope model) including sex, age, height, and stratification factor as covariates and a random intercept and slope. The treatment effect is determined by using estimated average slopes for each treatment group on the basis of the treatment*time interaction term from the above mixed model, with time as a continuous factor and treatment as a categorical factor. All available FVC values from baseline to Week 52 will primarily be used, including those from the ETD visit for subjects who discontinued early and do not complete their study visits up to Week 52.
- As a secondary analysis, the same model will be fit using all data until the end of the study.
- The proportion of subjects who have an absolute decline $\geq 10\%$ in %FVC at least once during the study or who die will be analyzed using logistic regression including sex, age, height, and stratum as factors using data up to Week 52.
- In addition, the same will be presented using all data up to the end of the study. A time-to-event analysis may also be used to analyze the composite endpoint of %FVC decline and mortality up to the end of the study.
- The %FVC change from baseline will be analyzed using a similar random coefficient regression model (linear slope model) as FVC in mL.

- Other spirometry endpoints will be summarized descriptively, similar to FVC.

Sensitivity analyses including multiple imputation methods and a per-protocol analysis will be performed to assess the impact of missing data, noncompliance, and protocol violations on the primary efficacy analyses. Additional exploratory analyses and graphical presentations may be performed when deemed useful to better understand the data. Details will be described in the SAP.

Time-to-event Data (Including Hospitalization, First Acute IPF Exacerbation, Mortality, and [Qualifying for] Lung Transplant), Using All Data up to the End of the Study

- Time-to-event endpoints will be graphically presented by Kaplan-Meier estimates. In addition, a Cox proportional-hazards model with terms for age, sex, height, and stratum will be used to analyze the hazard ratios for each dose compared to placebo.

Other Efficacy Endpoints

- A mixed-effects model with treatment, time (as a categorical factor), treatment*time, and baseline total score as factors in the model will be applied to the change from baseline in SGRQ total score.

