A mixed-effects model with treatment, time (as a categorical factor defined by the analysis windows in Section 6.3), treatment\*time, and baseline total score as factors in the model will be applied to the SGRQ total score change from baseline. LS means (with 95% CI) will be estimated from the model at each time point for each treatment group as well as the differences from placebo in LS means (and 95% CIs). This model will be used to calculate the p-values for the SGRQ total score (key secondary endpoint) to use in the multiplicity adjustment.

A patient is an SGRQ responder if his absolute change from baseline in SGRQ total score is  $\leq$  -4 points. The number (%) of SGRQ responders at each analysis time point up to the end of the study will be presented and a logistic regression will be used to analyze the data similarly as described above for FVC responders.

In addition, a cumulative incidence table and graph will be presented for absolute change from baseline in total SGRQ score per time point and worst-case up to the end of the study for the categories  $\leq$ -4,  $\leq$ -3,  $\leq$ -2,...,  $\leq$ 0, ...,  $\leq$ 2,  $\leq$ 3,  $\leq$ 4, by treatment group.

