## 3. ADDITIONAL DETAILS ON MIXED-EFFECT MODEL FOR REPEATED MEASURES ANALYSIS

A mixed-effects model for repeated measures (MMRM) with treatment\*time (categorical), stratum, gender, age, height and baseline value as factors in the model will be applied to the change from baseline in FVC value in mL. Least squares (LS) means (with 95% CI) will be estimated from the model at each time point for each treatment group as well as the differences from placebo in LS means (and 95% CIs).

The SAS code for the MMRM model for FVC change from baseline is given below. The same model will be used for SGRQ.

proc SORT data= FVC;

BY patient visit;

run;

proc MIXED data=FVC order=internal covtest ;

CLASS patient treatment visit;

MODEL change\_from\_baseline= treatment\*visit baseline gender age height stratum /solution ddfm=KR;

```
REPEATED visit/type=UN subject =patient;
```

```
LSMEANS treatment*visit / cl diff;
```

run;

If the model does not converge with an unstructured variance-covariance model, other structures will be tried (e.g. heterogenous Toepliz, AR(1),...). The structure with the best fit, based on Akaike's information criterion, will then be used.

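### SAP 9.3.5 and Appendix 3 give different covariates for the SGRQ model behind a key secondary p-value; the Appendix 3 CLASS statement and the 9.3.10 subgroup wording also need correction

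*SAP*

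**What the plan says.** **SGRQ.** SAP 9.3.5 lists treatment, categorical time, treatment*time "and baseline total score as factors in the model will be applied to the SGRQ total score change from baseline". It adds: "This model will be used to calculate the p-values for the SGRQ total score (key secondary endpoint) to use in the multiplicity adjustment". Protocol 7.3.4 has the same terms: "and baseline total score as factors in the model will be applied to the change from baseline in SGRQ total score". SAP Appendix 3 describes a repeated-measures model with treatment*time and "stratum, gender, age, height and baseline value as factors in the model", and says: "The same model will be used for SGRQ". Appendix 3 is also the only place that gives a covariance structure usable for SGRQ ("REPEATED visit/type=UN subject =patient").

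**Stratification.** SAP 7.6 says the analyses are stratified by standard of care at randomization: nintedanib, pirfenidone or neither.

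**FVC repeated-measures model.** SAP 9.3.2.2.1 lists stratum and baseline beside treatment and time, and refers to Appendix 3 for details. Appendix 3 adds gender, age and height. Its code has "CLASS patient treatment visit" and then, in the MODEL statement, "baseline gender age height stratum /solution ddfm=KR". The Appendix 1 code for the primary model does list gender and stratum in CLASS.

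**Subgroups.** SAP 9.3.10 names rate of decline in FVC as the endpoint, adds a treatment-by-subgroup term to a similar random coefficient model, and plots LS mean differences. SAP 9.3.2.1 separately promises a similar analysis by standard of care.

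**What is still live.** The 9.1 list of omitted analyses drops only the per-protocol and slope analyses of SGRQ, does not drop 9.3.2.2.1, and removes every listed subgroup except stratum.

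**The concern.** A confirmatory p-value should come from one model that is fixed in advance. Here a programmer who follows 9.3.5 and one who follows Appendix 3 would fit different models, each with support in the SAP. SAP 2.7 says part of the study team was unblinded after the decision to stop, so an undocumented choice between two printed models would be hard to defend.

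The Appendix 3 code cannot run as the text intends. PROC MIXED would stop on a character stratum variable, and would fit a numeric one as a linear score over three unordered categories.

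The 9.3.10 forest plot by stratum is meant to show whether the effect on FVC decline differs by background therapy. If its contrast is coded as a level difference, it does not answer that question.

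**Working it through.** The documents give no figure for these models, so there is none to reproduce. The check compares the texts and then sizes the consequences.

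**1. SGRQ covariates**

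| Source | Terms beyond treatment, time, treatment*time |
|---|---|
| Protocol 7.3.4 | baseline |
| SAP 9.3.5 | baseline |
| SAP Appendix 3 | baseline, stratum, gender, age, height |

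Writing treatment*visit without main effects, as Appendix 3 does, is the same mean model reparameterized, so only the covariates differ. With the Week 26 and Week 52 windows, the fixed-effect parameters number 7 under 9.3.5, 12 under the Appendix 3 text (stratum 2, gender, age and height 1 each), and 11 under the Appendix 3 code with a numeric stratum.

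The other inferential models carry stratum: the primary slope model (9.3.2.1), the progression logistic model (9.3.2.3, factors similar to the FVC model), the hospitalization Cox model (9.3.3) and the FVC repeated-measures model (9.3.2.2.1). Section 9.3.5 is the exception.

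Size: no R-squared is given, so assume that stratum plus sex, age and height explain 2%, 5% or 10% of variance.
- SE ratio = sqrt(1 − R²) = 0.990, 0.975, 0.949. In simulation, after paying for the extra parameters, the adjusted SE is smaller by 0.7%, 2.2%, 4.9%.
- With the same point estimate, a 9.3.5 result of p = 0.042 (z = 2.033) becomes z = 2.033/0.990 = 2.054, p = 0.040 at R² = 2%; p = 0.037 at 5%; p = 0.032 at 10%.
- In 20,000 simulated null trials per setting (250 per arm, Week 52 ANCOVA), the two models give opposite verdicts in 0.85%, 1.32%, 1.76% at the 4% level (600 mg) and 0.30%, 0.32%, 0.49% at the 1% level (200 mg).

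These rates are unconditional. SAP 9.3.1 requires success on the primary, progression and hospitalization endpoints for that dose first.

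**2. CLASS statement**

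Suppose one of three equal strata differs from the other two. A linear score captures 0% of the between-stratum variation if the odd stratum has the middle code. At an end code it captures 75%: for means 0, 0, 6 the total sum of squares is 24 and the regression sum of squares is 18.

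Effect on the Week 52 SE: SE = sqrt(2 × V52/250), where V52 is the residual variance at Week 52. Inputs are SD 275 mL (protocol 7.1), 52-week declines of 120 and 200 mL for nintedanib and pirfenidone (rounded from protocol 4.2), an assumed 232 mL for neither (equal to 120 plus the 112 mL nintedanib effect in protocol 7.1), equal strata, and an assumed random-slope SD of 200.
- No stratum: sqrt(2 × 275²/250) = 24.60 mL.
- Stratum in CLASS: 24.48 mL. The gain is small because a main effect that is constant over visits absorbs only part of a gap that grows with time.
- Linear score: 24.49, 24.54 or 24.59 mL by code order. The worst loss is 24.59/24.48 − 1 = 0.4%.
- With slope SD 150 to 230 and strata equal or 40/40/20, the worst code order costs 0.1% to 0.7% for a decline of 150 to 232 mL in neither, and 0.5% to 1.4% at 300 mL.

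**3. Section 9.3.10 read literally**

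In Appendix 1, treatment enters only through time. Add a treatment-by-stratum level term δs and keep one slope difference β. The LS mean difference in stratum s at time t (years) is then δs + β·t.

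Assume true slope effects of 0, 0 and 120 mL/year, equal strata, and SDs of 600 (intercept), 200 (slope) and 150 (residual). Noise-free GLS gives β = (0 + 0 + 120)/3 = 40 and δ = −5.2, −5.2, +10.4.
- At mean visit time (Week 19.8, t = 0.381): 10.0, 10.0, 25.6 mL.
- At Week 52: 34.8, 34.8, 50.4 mL.

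A true gap of 120 mL/year shows as 15.6 mL (11 to 22 mL over four variance settings). With strata 40/40/20, β = 0.2 × 120 = 24 and the gap is unchanged. A treatment*time*stratum model returns 0, 0, 120.

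**The case against.** Three objections have weight.

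First, the protocol and 9.3.5 agree with each other, and 9.3.5 states outright that its model supplies the p-value, so one could treat the Appendix 3 sentence as loose drafting. That is a fair argument for the smaller model. But it leaves SGRQ as the one inferential model without the randomization factor, against 7.6, and it leaves the SGRQ covariance structure resting on the sentence being set aside. The 7.6 clause about exceptions concerns which stratum value is used and does not clearly exempt 9.3.5.

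Second, the CLASS omission is a slip whose intended coding is clear from Appendix 1. A character variable would expose it at once, and its cost is trivial. This stands.

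Third, the literal reading of 9.3.10 is not the likeliest one. The section names rate of decline, and treatment enters the Appendix 1 model only through time, so an interaction with treatment would naturally be an interaction with slope. The literal model even implies arm differences at time zero. Section 9.3.2.1 also plans by-stratum slopes. This stands too: the remaining point is that 9.3.10 does not say which contrast it plots.

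A reader might infer that the SGRQ covariates were changed after results were known. The documents do not support that. The version history lists no SGRQ model change, and the 9.1 table lists omitted analyses, so its silence on covariates shows little.

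**Conclusion.** The SGRQ inconsistency is real and should be resolved, as a minor point. Two incompatible covariate sets are given for the model behind one key secondary p-value, and the set in 9.3.5 also departs from 7.6. The FVC repeated-measures covariates disagree between 9.3.2.2.1 and Appendix 3, and the Appendix 3 code does not implement its own text for stratum.

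The consequence is limited. Verdicts differ in about 1% to 2% of null trials at the 4% level, and in at most about 0.5% at the 1% level, under assumed R² values and before conditioning on the earlier tests. The CLASS slip costs 0.4% of the SE in the main case and 1.4% at worst. SAP sections 1 and 9.1 already state that no treatment effect was observed, so the confirmatory SGRQ test is very unlikely to be reached, though its estimate and interval will be reported.

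Two stronger readings are not supported. A reader might infer that one SGRQ model is biased or inflates the error rate, but under randomization both are valid and they differ in precision. A reader might also infer that the plan has no by-stratum slope analysis or would conceal differences between strata. Section 9.3.2.1 plans that analysis, and the level-difference result in 9.3.10 follows only from a literal reading that was probably not intended. Confidence is high on the covariate and CLASS points and lower on 9.3.10, which is a wording query.

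**What to change.** - **SGRQ:** print one fixed-effects set in both 9.3.5 and Appendix 3. The Appendix 3 set, with stratum, agrees with 7.6 and the other inferential models and adjusts for the randomization factor. Report the protocol 7.3.4 / 9.3.5 model beside it. Keep the Appendix 3 covariance structure, degrees-of-freedom method and fallback rule for SGRQ.
- **Record:** note the departure from protocol 7.3.4 and its reason in 9.1 or, because part of the team is unblinded, in the CSR, as 9.1 requires for changes after unblinding.
- **FVC repeated-measures model:** make the covariates identical in 9.3.2.2.1 and Appendix 3.
- **Code:** use `CLASS patient treatment visit gender stratum;` in Appendix 3.
- **Section 9.3.10:** state that by-stratum effects are slope differences, taken either from treatment*time*stratum (with stratum and stratum*time) or from separate fits per stratum, and name the same choice in 9.3.2.1.

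Cost: a few lines of text, one CLASS statement, a set of ESTIMATE statements, one extra SGRQ model fit and one documented entry. No new data are needed and the primary test is unchanged.

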- The change from baseline in DLCO will be analyzed similarly as change in SGRQ.
- EQ-5D, SGRQ total score and domains, LCQ total score and domains, K-BILD total score and domains, and VAS Cough and Urge to Cough will be presented using descriptive statistics by treatment group of actual values and changes from baseline at all time points. The proportion of SGRQ responders (defined as absolute change from baseline at all time points in SGRQ total score ≤ -4 points) will also be tabulated by treatment group.
- The proportion of SGRQ responders and the proportion of subjects with hospitalization will be analyzed using a logistic regression model similarly as described above and presented by treatment group.
- The actual values and changes from baseline of 6MWT [REDACTED] will be presented descriptively for each time point by treatment group.

[REDACTED]

More details will be described in the SAP.

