# 9.3.2.1. Primary Endpoint: Rate of Decline in FVC over a Period of 52 Weeks

The primary endpoint of annual rate of decline in FVC at Week 52 (in mL) will be analyzed, including data up to and including the 52-week analysis window defined in Section 6.3. A random coefficient regression model (linear slope model) will be used including sex, age, height and stratification factor as covariates and a random intercept and slope. The treatment effect is determined by using estimated slopes for each treatment group on the basis of the time-by-treatment interaction term from the mixed model. All available FVC values (as defined by the analysis windows) from baseline to Week 52 will be used including FVC measurements at the follow-up visit for subjects who discontinue IP prematurely and do not complete the study visits through Week 52. The model will be fit using the SAS PROC MIXED procedure, details are in Appendix 1.

The assumptions of the model will be investigated.

The same model will be used for the pooled analysis for the integrated summary of efficacy adjusted for study. More detail will be in a separate SAP.

A similar analysis will also be provided by stratification factor (standard of care).

The percent predicted FVC will be analyzed using a similar random coefficient regression model (linear slope model) as FVC expressed in mL.

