# 9.3.2.3. First Key Secondary Endpoint – Disease Progression

Disease progression is defined as the composite endpoint of first occurrence of  $\geq 10\%$  absolute decline in percent predicted forced vital capacity (%FVC) or all-cause mortality at 52 weeks. The number (%) of subjects who experience disease progression up to Week 52 will be presented and analyzed using logistic regression with similar factors in the model as for FVC rate of decline. The odds ratios (with 95% CI) versus placebo will be estimated from the model. This analysis corresponds to the key secondary endpoint and will be used in the multiplicity approach.

A similar summary analysis will also be provided by stratification factor (standard of care).

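### The SGRQ responder logistic regression leaves out baseline SGRQ, which the SGRQ mixed model includes; if baseline predicts response, the omission costs some power

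*SAP*

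**What the plan says.** The covariates of the responder model have to be traced through cross-references.

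- **SAP 9.3.5 (responders).** For responder status at each analysis time point, "a logistic regression will be used to analyze the data similarly as described above for FVC responders". No covariates are listed there.
- **SAP 9.3.2.3 (disease progression).** This is the only FVC logistic model described earlier. It is "analyzed using logistic regression with similar factors in the model as for FVC rate of decline", and it reports odds ratios against placebo with 95% confidence intervals.
- **SAP 9.3.2.1 (FVC slope).** The factors referred to are given as "including sex, age, height and stratification factor as covariates and a random intercept and slope".
- **Protocol 7.3.4.** The progression endpoint "will be analyzed using logistic regression including sex, age, height, and stratum as factors using data up to Week 52". Further on: "The proportion of SGRQ responders and the proportion of subjects with hospitalization will be analyzed using a logistic regression model similarly as described above".
- **SAP 9.3.5 (continuous score).** The mixed model has treatment, time, their interaction "and baseline total score as factors in the model will be applied to the SGRQ total score change from baseline". SAP Appendix 3 also has a baseline term, adds stratum, gender, age and height, and says that its model applies to SGRQ.

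The p-value for the testing hierarchy comes from the mixed model. SAP 9.1 drops only the per-protocol analysis and the random coefficient model from 9.3.5, so the responder regression is still to be run.

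**The concern.** Responder status is the SGRQ change from baseline cut at -4 points on a 0 to 100 scale. The SAP adjusts that change for baseline when it is analysed as a continuous variable. When the same change is dichotomised, the covariates come from an FVC model with no SGRQ term. Neither document gives a reason, and a borrowed cross-reference is the likeliest explanation.

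If the baseline score predicts who responds, leaving it out discards information that the trial already holds: SGRQ is collected at Visits 1 and 3, and the baseline value is needed to define a responder at all. What is at stake is some power in a supportive comparison. There is also a smaller problem of wording. SAP 9.3.5 points to an analysis of FVC responders, but nothing earlier carries that name, so two programmers could fit different models.

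**Working it through.** **Plan's own figure.** There is none. The documents give no responder rate, SD, baseline-change correlation or power for SGRQ, so the effect was examined by simulation.

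**Inputs from the documents.** 250 subjects per arm (Protocol 7.1); two-sided 4%, the level for 600 mg against placebo (SAP 9.3.1), used as a yardstick because the responder analysis has no assigned alpha; response defined as change of -4 or lower (SAP 9.3.5); planned covariates sex, age, height and stratum.

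**Assumed inputs.** SD of change 14; placebo mean change +3; treatment effect -4 points, so active mean change -1; correlation of baseline with change (rho) from 0 to -0.5; no effect of sex, age, height or stratum on response.

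**Hand check without baseline.**

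- Placebo response: Phi((-4 - 3)/14) = Phi(-0.50) = 0.309.
- Active response: Phi((-4 + 1)/14) = Phi(-0.214) = 0.415.
- Log odds ratio: ln(0.415/0.585) - ln(0.309/0.691) = -0.343 + 0.805 = 0.46.
- SE: sqrt[1/(250 x 0.309 x 0.691) + 1/(250 x 0.415 x 0.585)] = sqrt(0.0187 + 0.0165) = 0.188.
- z = 0.46/0.188 = 2.45. Against the critical value 2.054, power is Phi(0.40), about 66%.

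The simulation agrees with this: log odds ratio 0.466 to 0.476, SE 0.190 and power 65% to 68% without baseline.

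**Simulation.** 2,000 trials per correlation. Each trial was fitted with treatment and the four planned covariates, then again with baseline SGRQ added.

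| rho | log OR without / with | SE without / with | Power at 4%, without / with | Equivalent sample size gain |
|---|---|---|---|---|
| 0 | 0.468 / 0.469 | 0.190 / 0.191 | 66.6% / 66.2% | 0% |
| -0.2 | 0.476 / 0.490 | 0.190 / 0.193 | 67.2% / 68.4% | 3% |
| -0.3 | 0.474 / 0.502 | 0.190 / 0.197 | 67.0% / 69.5% | 5% |
| -0.4 | 0.472 / 0.524 | 0.190 / 0.201 | 67.8% / 72.4% | 10% |
| -0.5 | 0.466 / 0.556 | 0.190 / 0.209 | 65.2% / 72.8% | 18% |

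The last column is (mean z with / mean z without)^2 - 1. At rho = -0.5, for example, (0.556/0.2087)^2 / (0.466/0.1901)^2 = (2.664/2.451)^2 = 1.18. The Monte Carlo error of one power figure is about sqrt(0.67 x 0.33/2000) = 1.05 points. At two-sided 5% the pattern is the same: 70.1% to 69.8% at rho 0, and 69.0% to 75.9% at rho -0.5.

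**Where the gain comes from.** The SE of the log odds ratio goes up with adjustment. Power rises because the conditional log odds ratio moves further from zero than its SE grows.

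**Risk-difference scale.** For a risk difference standardised over baseline (3,000 trials per setting, baseline the only covariate), the variance ratio, adjusted to unadjusted, was 1.00, 0.98, 0.90 and 0.84 at rho 0, -0.2, -0.4 and -0.5. There is a precision gain on that scale, but the SAP does not plan such an estimate.

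**Type I error.** With no treatment effect and rho = -0.4, rejection at nominal 4% was 4.2% without baseline and 3.8% with it. Both are within Monte Carlo error of 4%, which is sqrt(0.04 x 0.96/2000) = 0.44 points.

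**The case against.** **The SAP never states that baseline is excluded.** This is correct. The covariate set is reached through wording of the kind similar or similarly, and the FVC label plainly means the progression model. But neither document names baseline SGRQ for the responder model, and the model referred to has no baseline term. Following the text gives a model without it.

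**The analysis hardly matters.** This largely stands. Responder status is not among the key or other secondary endpoints in SAP 2.2, the hierarchy uses the mixed model that already adjusts for baseline, and the SAP says that no treatment effect was observed and an abbreviated report will follow. That makes the point minor; it does not justify the omission.

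**The size rests on assumptions.** This stands. At a correlation of zero there is no gain, and at -0.2 it is about one power point. A floor effect adds little: with an assumed baseline mean of 40 and SD of 18, the share of subjects scoring below 4, who cannot respond, is Phi((4 - 40)/18) = Phi(-2) = 2.3%.

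A reader might also infer more than the documents support:

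- *That the odds ratio loses precision.* Adjustment widens the SE of the log odds ratio that the SAP would report.
- *That the comparison is biased or its error rate inflated.* Randomisation protects it, and the null simulation shows no inflation.
- *That adding baseline makes the odds ratio comparable with the mean SGRQ difference.* The two are on different scales whatever the covariates.

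**Conclusion.** The point holds as a minor one. As the SAP and protocol read, the SGRQ responder regression carries the FVC covariates and omits baseline SGRQ total score, in contrast with both SAP descriptions of the SGRQ mixed model. The cost is power only: about 0 to 8 points at two-sided 4% with 250 per arm, or roughly 0 to 18% in equivalent sample size, over assumed correlations of 0 to -0.5. The figure depends mainly on that correlation, which the documents do not give, and also on the assumed SD, mean change and effect. If baseline is only weakly related to change, the loss is negligible. No confirmatory conclusion is affected.

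**What to change.** In SAP 9.3.5, replace the cross-reference with an explicit model: logistic regression with treatment, stratum, sex, age, height and baseline SGRQ total score (continuous), fitted at each analysis time point, with the odds ratio against placebo and its 95% confidence interval reported as conditional on these covariates.

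This costs one covariate in a planned model and no new data. It has two downsides. The log odds ratio will have a slightly larger SE (0.191 to 0.209 against 0.190 in the simulation) and is a conditional quantity, so it should not be read as the crude odds ratio. In addition, SAP 2.7 says that part of the study team was unblinded after termination. The change and its reason should therefore be recorded in the study report, as SAP 9.1 already requires for changes after unblinding.
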